**Nourishing the Community Through Culinary Medicine- Acres Homes**

**NCT06096506**

**Version Date: 04/08/2024**

Protocol Title:	Nourishing the Community Through Culinary Medicine- Acres Homes
Principal Investigator:	[name], MPH, Assistant Professor, Department of Health Promotion and Behavioral Sciences
Study Coordinator:	[name]
Population:	132 adult patients (18-75 years) with type 2 diabetes and elevated body mass index receiving care from UT Physicians clinics
Number of Sites:	Various UT Physicians clinics- single system
Study Duration:	October 2023 to September 2024
Subject Duration:	12 months participation with approximately 3 months of active participation and the remainder of time for passive follow-up on patient outcomes via electronic medical records.

---

## General Information

- Nourishing the Community Through Culinary Medicine Study is a pilot study to implement a virtual culinary medicine intervention to low income, ethnically diverse adults with diabetes and elevated body mass index. A pre-post survey design and clinical electronic medical record data (HbA1c, Body Mass Index, Blood Pressure, HDL, LDL and Triglycerides) will be used to evaluate patient outcomes.

## Background Information

- Over 34 million (13%) adults in the United States (US) have diabetes mellitus (DM), with rates climbing over 26% among adults aged 65 years or older and disproportionately higher rates among many Texas residents. (CDC, 2020; Schuler & Koka, 2019). The disparity grows stark when broken down by age among Texas residents, with 42% and 53.9% of adults aged 45 or older suffering from DM in the Dallas and Houston regions respectively (BRFSS, 2018). Further, adults with DM carry a 50% higher risk of mortality, have more health complications, and spend more than \$9,500 yearly on medical costs than their counterparts. (Rowley, 2017). In addition, the CDC estimates more than 34% of adults are currently afflicted with pre-diabetes and at risk of developing DM. Alarming, the prevalence of DM is forecast to increase by more than 50% over the next decade (Rowley, 2017).
- Although consuming a healthy diet is a well-supported and low-cost approach for reducing the risk of Type 2 DM (Hu et al., 2020), less than 10% of adults in the U.S. actually follow this approach (USDA 2015; Wilson et al., 2016). Low levels of food literacy coupled with poor dietary consumption behaviors among the US population warrant the need for innovation in nutrition education and intervention approaches (Downer et al., 2020; Etherton et al., 2014; Van Horn et al., 2019). Culinary Medicine (CM) is an emerging educational and nutritional approach that adds to current nutrition education and interventions by incorporating both, the practical hands-on preparation skills and pleasure of food, and the scientific knowledge of how nutrition and dietary patterns affect health outcomes (Birkhead, et al., 2014; La Puma et al., 2016; Polak et al., 2016; Barkoukis et al., 2019).

- There is currently a critical gap of evidence-based “how-to” nutrition information that is tailored for culturally diverse, low-income minority populations across Texas. Furthermore, lifestyle interventions are needed to mitigate chronic disease such as type 2 DM among low-income minority populations, who are at a disproportionately higher risk for these conditions. This can be done by strengthening clinic-community linkages to offer lifestyle-based prevention services for their patients. We will build upon existing resources at UTH Health Nourish program (McWhorter et al., 2019) which implements interdisciplinary evidence-based CM curricula across sectors in Harris County.

## Objectives

- The purpose of this study is to implement a five-session hands-on virtual CM program (to be held weekly or bi-weekly) among patients with diabetes and elevated body mass index receiving care UT Physicians clinics serving the Acres Homes neighborhood, and comparing their outcomes to patients in usual care from UT Physicians clinics outside of the Acres Homes service area.
- The overall goals of this project are to:
  - To implement adapted virtual CM curriculum among target population
  - To assess if program participation improves participant dietary behaviors, nutrition knowledge, and cooking skills and behaviors above standard of care.
  - To assess if program participation improves patient levels of HbA1c, Body Mass Index, Blood Pressure, HDL, LDL and Triglycerides above standard of care.
  - To assess if social determinants of health modify the association between participating in the program and any of the aforementioned outcomes.
  - To determine the feasibility and reproducibility of virtual synchronous CM classes.

## Study Design

- This study is a pilot study with a quasi-experimental design using assigned intervention and control clinics.
- Study participants will be evaluated prior to and immediately after the program via pre and post survey.
- EMR data will be reviewed at baseline and completion of program
- This one-year project will include:
  - a) conducting the virtual CM program for approximately 66 intervention patients with diabetes receiving care at UT Physician Clinics serving the Acres Homes neighborhood in Houston
  - b) conducting program evaluation (pre- and post-test surveys and EMR data) using data from those 66 intervention participants and 66 control participants recruited from UT Physicians clinics outside of the Acres Homes service area
- The pre-post survey will evaluate participants’ dietary behaviors, nutrition knowledge, cooking skills and behaviors along with demographic information. The EMR data will evaluate improvements in clinical data: HbA1c, Body Mass Index, Blood Pressure, HDL, LDL and Triglycerides. The results will be used to determine if virtual CM education can be effective in improving certain health outcomes, dietary behaviors and cooking-related constructs.
- There are a few minimal risks known to taking part in this study. Knives will be utilized raising the risk for minor cuts. Stove tops, ovens, microwaves, and other kitchen equipment will be utilized raising the risk for minor burns. Food items containing known allergens will be utilized raising the risk for allergic reaction. We anticipate participation in this study to be of minimal risk and do not expect our program or surveys to cause emotional distress.

## Study Population

- It is anticipated that program participants will be low-resource and ethnically diverse, reflective of UT Physicians patients at the clinics serving the Acres Homes neighborhood of Houston.
- Inclusion Criteria:
  - Receiving care at UT Physicians clinics;
  - Adult patients (18 to 75 years) diagnosed with type 2 diabetes and elevated body mass index ( $\geq 25$ );
  - HbA1c labs and clinic-assessed weight completed within the last 3 months;
  - English speaking or Spanish speaking.
  - Can obtain groceries before each class (intervention group only)
- Exclusion Criteria:
  - Patients without the technological support needed to participate (e.g., reliable internet and device - cell phone, tablet or laptop);
  - Patients with an uncontrolled impairment that interferes with ability to participate.
- Recruitment: Patients meeting the aforementioned inclusion criteria will be invited to participate. We will conduct separate recruitment for intervention and control participants- with the intervention participants recruited from the Victory and Greens UT Physicians clinics that serve Acres Homes, and control participants recruited from the Jensen UT Physicians clinic. Jensen has a similar patient population to Victory and Greens, and is relatively close geographically, while still sitting outside of the target neighborhood of Acres Homes. UT Physicians' care coordinators will assess patient eligibility to participate in the program and share either a flyer or an interest form link with eligible patients. Patients will complete the interest form giving UTHHealth their contact information. UTHHealth staff will reach out to patients and explain the program (time commitment, class days/time). If patient is interested, UTHHealth study staff will perform a technology screening since all classes will be held virtually. After screening, UTHHealth will send an online informed consent and pre-survey.

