### **Statistics**

- 132 participants are planned to be enrolled, 66 from intervention clinics and 66 from control clinics.
- All participants that enroll in the program will be included in the analysis. Saturation point is considered attendance of 4 out of 5 sessions (80%).
- Statistical analysis will include descriptive and frequency analysis of responses, a pre-post analysis using paired t-test, chi-square test, and Analysis of Covariance to determine changes in biometric and behavioral measures pre to post NCCM program participation.
- Level of significance will be set at  $p < 0.05$ .
- Qualitative data will be analyzed for themes using standard methods and NVivo software. Responses will be summarized, and a report will be created to provide information to our research investigators and the public health community.

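### The grocery-access criterion applies to the intervention arm only, an avoidable selection difference in a non-randomised comparison whose size and direction the documents cannot settle

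*Combined protocol and SAP*

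**What the plan says.** The protocol's Study Design section states: "This study is a pilot study with a quasi-experimental design using assigned intervention and control clinics". Under Recruitment in Study Population it adds: "We will conduct separate recruitment for intervention and control participants". Intervention patients come from the Victory and Greens clinics and control patients from Jensen. The case for comparability is one statement, given without figures: "Jensen has a similar patient population to Victory and Greens, and is relatively close geographically".

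The inclusion list in the same section contains "Can obtain groceries before each class (intervention group only"). Care at the clinics, age, diabetes and body mass index, recent HbA1c and weight, and language all apply to both arms. So do the exclusions for lack of technology and for an uncontrolled impairment.

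The comparison is meant to be between arms. One goal in Objectives reads: "To assess if program participation improves patient levels of HbA1c, Body Mass Index, Blood Pressure, HDL, LDL and Triglycerides above standard of care". HbA1c is the primary outcome, and dietary measures are among the secondary outcomes. The Statistics section gives the enrolment: "132 participants are planned to be enrolled, 66 from intervention clinics and 66 from control clinics". It names analysis of covariance but no adjustment covariates.

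**The concern.** Without randomisation, a between-arm comparison is easier to defend when both arms are drawn by the same rules, so that a control is someone who could have entered the program. Here a patient who cannot obtain groceries is screened out at Victory or Greens but can be enrolled at Jensen. The statement that the clinics serve similar patients does not address this, because it describes clinic populations and the criterion acts on individuals within one arm.

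The exclusion for lack of technology makes the contrast plain. It too concerns the ability to take part in virtual classes, yet it is written for both arms. The plan therefore already screens controls on one class-participation requirement and does not do so for groceries.

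At stake is how an arm difference in HbA1c or diet is read. Part of it could reflect who was admitted to each arm, and as planned nothing recorded in controls would show how large that part is.

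**Working it through.** **The plan's own figures.** Enrolment agrees: 66 + 66 = 132. The documents give no target difference, standard deviation, power or dropout, so no detectable difference can be reproduced from them.

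**Is the difference repaired elsewhere?**
- *Covariates.* The baseline covariate table lists food insecurity, internet access, health literacy and housing insecurity. The food-insecurity example item concerns worry about money for food, so it overlaps with the ability to obtain groceries only in part.
- *Grocery card.* Study Procedures gives program participants $40 per class for 5 classes, 5 × $40 = $200. This covers ingredient cost. The criterion may then act mainly through transport, store access or time, although the documents do not define it that closely.
- *Analysis.* With no covariates named, even partial adjustment for food insecurity is not prespecified.

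**Formula.** Let p be the share of enrolled controls who could not meet the criterion. Let D be how much worse their usual-care HbA1c change is than that of other controls. If the program has no effect and the arms are otherwise alike, the arm difference shifts by

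bias = p × D.

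**Illustration.** All inputs here are assumptions: p from 10% to 30%, D from 0.3 to 0.5 points.
- Low end: 0.10 × 0.3 = 0.03 points.
- High end: 0.30 × 0.5 = 0.15 points.

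**Scale.** The difference detectable with 80% power at two-sided 0.05 is (1.960 + 0.842) × SD × √(1 − r²) × √(2/66). Assume a baseline to follow-up correlation r = 0.6, so √(1 − r²) = 0.8. Also √(2/66) = 0.1741.
- SD 1.2: standard error 1.2 × 0.8 × 0.1741 = 0.167; detectable difference 2.802 × 0.167 = 0.47.
- SD 1.5: standard error 1.5 × 0.8 × 0.1741 = 0.209; detectable difference 2.802 × 0.209 = 0.59.

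The mid-range bias, 0.20 × 0.4 = 0.08, is 0.08/0.209 = 0.38 to 0.08/0.167 = 0.48 of a standard error.

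**Wider assumed ranges.** Take p from 5% to 30%, D from 0.3 to 1.0, and SD from 1.0 to 1.5 without baseline adjustment, so the standard error is SD × √(2/66), or 0.174 to 0.261. The chance of a significant result when the program has no effect is P(|Z + pD/SE| > 1.96). Each cell gives the bias, then that chance for SD 1.5 to SD 1.0.

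| p | D = 0.3 | D = 0.5 | D = 1.0 |
|---|---|---|---|
| 5% | 0.015; 0.050–0.051 | 0.025; 0.051–0.052 | 0.05; 0.054–0.060 |
| 15% | 0.045; 0.053–0.058 | 0.075; 0.060–0.072 | 0.15; 0.089–0.138 |
| 30% | 0.09; 0.064–0.081 | 0.15; 0.089–0.138 | 0.30; 0.210–0.407 |

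At 5% the nominal 0.05 is almost unaffected. At 30% with a large D it is not. The documents do not say which row applies.

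**The case against.** The criterion is a feasibility condition. Controls attend no classes, so taken literally it has no meaning for them, and with ingredient cost covered by the card it may exclude very few people. A stable access barrier should also show largely in baseline HbA1c, which paired tests and analysis of covariance remove or reduce. Bias then requires a different change over the follow-up, and the 0.3 to 0.5 points used above has no support in the documents. This is moreover a pilot, and separate clinics, separate recruitment and willingness to attend five 90-minute sessions would leave the arms differently selected anyway.

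Much of this stands. It explains why the criterion was written, it keeps the plausible size modest, and it means that the fix removes one source of selection among several. It does not show that the one-arm rule is harmless. Adjusting for baseline HbA1c does not remove a difference in later change. The Publication Plan also intends these data to support a full-scale trial.

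A reader might go further in two ways that the documents do not support.
- *That the bias favours the program.* This presumes that low-access controls do worse over follow-up. If they start with higher HbA1c, regression to the mean could make their change look better, so the direction is open.
- *That the social-determinants goal is blocked* ("To assess if social determinants of health modify the association"). Ability to obtain groceries is not a listed determinant, and the criterion excludes nobody on food insecurity, housing, literacy or internet access as measured. Applying it to both arms would leave modification by grocery access inestimable in any case.

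**Conclusion.** The point holds as an avoidable difference in selection. One eligibility rule that bears on diet is applied to one arm of a non-randomised, separately recruited comparison, and nothing in the plan clearly measures or adjusts for it. Its size and direction cannot be determined from the documents. A shift of about 0.03 to 0.15 HbA1c points follows only from the assumed 10% to 30% unable and 0.3 to 0.5 points worse change. It is negligible if few patients fail the criterion. The case for acting rests on how little the correction costs, since no large bias has been shown.

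**What to change.** In Study Population, delete the words that limit the grocery criterion to the intervention group. At screening, ask patients in both arms whether they could obtain a list of groceries weekly or every two weeks if given a $40 grocery card each time. Apply the answer to both arms from then on. The card must be part of the question. Otherwise controls may answer no because of cost, while program patients are judged for a program that pays, and the control arm would become the better resourced one.

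For controls already enrolled, ask and record the same question. Keep every enrolled control in the primary analysis, and prespecify a sensitivity analysis restricted to controls who would have met the criterion. Making the restricted set primary would rest the main result on hypothetical self-report given after enrolment and would lose those who do not answer. Report how many patients the criterion excludes in each arm, since that number shows whether the issue is material.

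The cost is one extra question, a short amendment and slightly fewer eligible controls. The planned 66 + 66 need not change.

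### With one control clinic and a programme taught in class cohorts, the arm comparison cannot be separated from a clinic difference, and the listed tests allow for neither clinic nor cohort

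*Combined protocol and SAP*

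**What the plan says.** Study Design describes a "quasi-experimental design using assigned intervention and control clinics", so the clinic and not the patient determines arm. Study Population has "intervention participants recruited from the Victory and Greens UT Physicians clinics that serve Acres Homes" and "control participants recruited from the Jensen UT Physicians clinic". The argument for comparability is that "Jensen has a similar patient population to Victory and Greens, and is relatively close geographically"; no data accompany it.

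Other sections speak of control clinics in the plural. Objectives compares the programme with "patients in usual care from UT Physicians clinics outside of the Acres Homes service area", and Statistics states that "132 participants are planned to be enrolled, 66 from intervention clinics and 66 from control clinics". Study Design uses the plural as well.

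Study Procedures describes live online classes run as English or Spanish cohorts. Compensation provides for people who repeat a class after an earlier cohort, so there is more than one cohort and some people may belong to two.

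Statistics lists paired t-tests, chi-square tests and ANCOVA at p < 0.05. It does not name the ANCOVA covariates. Nowhere does the protocol mention clinic or cohort as a model term, clustering, a mixed model or robust standard errors. On the use of the results, Study Design says: "The results will be used to determine if virtual CM education can be effective in improving certain health outcomes".

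**The concern.** The Objectives ask whether HbA1c and the other measures improve beyond standard of care, which is a between-arm question. Two features of the design affect the answer.

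The first is confounding. With a single control clinic, whatever is particular to Jensen goes wholly into the arm difference. HbA1c is taken from routine care with no study visits, so clinic-level differences in care or in the timing of tests could reach the primary outcome directly. Similar patients do not guarantee similar care.

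The second is clustering. People taught together may change together, and only the intervention arm has classes. A person-level test ignores this.

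The stake is that a modest difference between clinics, or a correct estimate with too small a standard error, is read as evidence that the programme works and is carried into the full-scale trial that the Publication Plan foresees.

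**Working it through.** **Inputs from the protocol:** 66 + 66 = 132, which adds up; two intervention clinics and one control clinic; significance level 0.05 (two-sided assumed). The 132 comes with no effect size, SD, power or dropout, so there is no derivation to reproduce.

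**Assumptions, because the protocol gives no figures:** a 33/33 split between Victory and Greens; clinic ICC (ρ) of 0.01, 0.02 or 0.05; 11 people per class; class ICC of 0.02 to 0.10; pre-post HbA1c correlation (r) of 0.5 to 0.8. Outcomes are on a scale with SD 1.

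**1. Person-level standard error.** Variance 2/66 = 0.0303; SE 0.174.

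**2. Clinic.** True variance = ρ(1/1 + 1/2) + (1 − ρ)(2/66). Real type I error of the person-level test = 2[1 − Φ(1.96 / SE ratio)].

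| ρ (adjusted outcome) | Variance | SE ratio | Type I error |
|---|---|---|---|
| 0.01 | 0.0150 + 0.0300 = 0.0450 | 1.22 | 11% |
| 0.02 | 0.0300 + 0.0297 = 0.0597 | 1.40 | 16% |
| 0.05 | 0.0750 + 0.0288 = 0.1038 | 1.85 | 29% |

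Simulation with 40,000 runs per setting gave 11%, 16% and 30%. The 1/2 is the sum of squared clinic shares in the intervention arm. An equal split makes that sum as small as it can be, so an unequal split would raise these figures.

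**3. The same ICC as a stable difference in HbA1c level.** ANCOVA on baseline leaves clinic variance ρ(1 − r)² and person variance (1 − ρ)(1 − r²).
- ρ = 0.02, r = 0.5: 0.0050 / (0.0050 + 0.7350) = 0.007, type I error 9%.
- ρ = 0.02, r = 0.8: 0.0008 / (0.0008 + 0.3528) = 0.002, type I error 6%.
- ρ = 0.05, r = 0.5: 0.0125 / (0.0125 + 0.7125) = 0.017, type I error 15%.
- ρ = 0.05, r = 0.8: 0.0020 / (0.0020 + 0.3420) = 0.006, type I error 8%.

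**4. Class clustering alone, intervention arm only.** Design effect = 1 + (11 − 1) × ICC; SE ratio = √[(design effect + 1)/2].
- ICC 0.02: design effect 1.2, ratio 1.05, type I error 6%.
- ICC 0.05: 1.5, 1.12, 8%.
- ICC 0.10: 2.0, 1.22, 11%.

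**5. Can a clinic term repair it?** Three clinics less two arms leaves 1 degree of freedom, with a critical t of 12.7. A clinic random effect is therefore not a usable remedy.

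**6. More control clinics.** With three in place of one, the clinic factor is 1/3 + 1/2 and the type I error for ρ = 0.01, 0.02 and 0.05 is 8%, 11% and 20%. That is lower, but still above 5%.

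**The case against.** The strongest objection is that the error rates rest on inputs that the protocol does not supply, and that the planned ANCOVA already deals with part of the problem. This stands. If clinics differ only in stable HbA1c level, step 3 replaces 16% with 6-9% and 29% with 8-15%. The higher figures apply only to an ICC for the baseline-adjusted outcome, that is, to clinic differences in change. Baseline HbA1c as covariate is itself a reading, since none is named.

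A related objection is that Jensen was chosen deliberately, so a type I error that treats clinics as random draws is a device for expressing what is really bias. That is fair, but the bias view gives the same message. If Jensen differed by a fixed 0.2 SD for reasons unrelated to the programme, the person-level test would be significant about 21% of the time (0.2/0.174 = 1.15; P(Z > 1.96 − 1.15) ≈ 0.21).

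The limitation is also partly disclosed. The study is called a pilot and quasi-experimental, all clinics belong to one system, and the Publication Plan speaks of preliminary data. Yet Study Design, where the pilot label appears, also says that the results will be used to determine whether the programme can be effective.

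Three stronger readings are tempting, and the documents do not support them:
- A reader might infer that the plan declares its 132 people independent, or that it promises confidence intervals that will be too narrow. It does neither. Independence follows only from the listed tests and the absence of any clustering term, and no confidence interval is mentioned.
- A reader might infer from the plural wording that further control clinics were intended and must now be recruited. The plural is general wording and the recruitment text is specific, so making the plurals singular would also reconcile them. The version is dated 04/08/2024 in a study running from October 2023 to September 2024. No section shows that another comparable clinic nearby exists.
- A reader might take specific differences in prescribing or laboratory practice at Jensen as fact. The documents report none.

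**Conclusion.** The point holds in two parts.

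Clinic and arm are confounded by design. This is certain, needs no assumed ICC, and cannot be undone in the analysis. Its size is unknown.

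The listed tests omit clinic and cohort, so the arm-comparison p-value is too small for any positive ICC. The direction is secure; the amount is illustrative. It runs from about 6% to 29% for clinic, depending on the ICC and on whether it describes change or a stable level, and from about 6% to 11% for class cohorts of 11. These figures should not be quoted as the trial's actual error rate.

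The two parts need different treatment. Cohort can be modelled. Clinic can only be disclosed and bounded.

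**What to change.** 1. **Statistics, primary analysis.** Make the between-arm HbA1c analysis an ANCOVA adjusted for baseline HbA1c, with class cohort as a random effect in the intervention arm only (a partially nested model). Eleven per class would mean about six cohorts (66/11), so prespecify a small-sample correction such as Kenward-Roger. Record cohort, and assign repeaters to their first cohort.
2. **Statistics, reporting.** Give the arm difference with a confidence interval, and a sensitivity interval that adds between-clinic variance at ICC 0.01, 0.02 and 0.05 of the adjusted outcome. Show Victory and Greens separately against Jensen.
3. **Study Design, conclusion.** Replace the statement that results will determine whether the education can be effective with: *give a preliminary estimate of the arm difference, which cannot be separated from clinic differences*.
4. **Wording.** Reconcile the plural control clinics in Objectives, Study Design and Statistics with the single clinic in Study Population. Adding control clinics is optional; it would reduce the problem without removing it.

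**Cost.** Items 1 to 4 need no extra patients, only analysis and wording, provided cohort is recorded. The price is a wider interval and a more modest conclusion. On the SD scale, before any allowance for cohort, the half-width goes from 1.96 × 0.174 = 0.34 to 0.42, 0.48 and 0.63 (1.96 × √0.0450, √0.0597 and √0.1038) at the three clinic ICCs. Optional extra control clinics would also need a protocol amendment, recruitment at a late stage and further record extraction.
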